1.3 Research Design

The following 3 groups of subjects will participate in all proposed studies of the Specific Aim #1: (1) SD patients; (2) SD/VT patients, and (3) healthy controls, who have no history of any neurological, psychiatric or laryngological problems. Because SD is a rare disorder, both ADSD and ABSD patients will be included to closely match with ADSD/VT and ABSD/VT patients, which will ensure the homogeneity between patient populations. Based on the reported SD clinical prevalence (Ludlow et al., 2008) and our own experience, we estimate that about 80% of the participating patients will have ADSD and 20% will have ABSD. SD patients only with VT without ET in other body parts will be recruited. Because the majority of VT patients report improvement of their voice symptoms after alcohol intake, we predict that at least 60% of recruited SD/VT group will also be ethanol-responsive. To further assure homogeneity between patient populations, we will carefully match SD and SD/VT patients according to their report of alcohol effects, in addition to their age, gender and an SD type match. Eligibility of patients will be established based on a three-tiered approach, including initial screening interview, detailed voice/speech, laryngological and neurological examinations (see *Appendices 1 and 2*), as previously described (Ludlow et al., 2008). Any subject with neurological (other than SD and SD/VT), psychiatric, or laryngological problem will be excluded from the study. All recruited patients must be symptomatic; if they are treated with botulinum toxin injections, they may be included only if they are symptomatic, that is at the end of their botulinum toxin treatment cycle. Controls will be carefully matched with SD and

SD/VT populations by their age and gender. Although we have a large neuroimaging database of SD patients and controls, those data were acquired by the PI on a different MRI scanner several years ago and, therefore, will not be used in the proposed studies to ensure the consistency in the scanner use and study design.

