1.3.1 Study #1: Mapping disorder-specific brain activation in patients with SD vs. SD/VT using fMRI during symptomatic voice and speech production. We will use a sparse-sampling event-related BOLD fMRI design on a 3.0 Tesla Philips MRI scanner. We already successfully used this design for the investigations of voice and other laryngeal behaviors (Loucks et al., 2007; [name] et al., 2007; [name] et al., 2009; [name] and Ludlow, 2010). Brain activity will be studied during production of 10 symptomatic speech sentences (e.g., "We eat eels every day", "Sam has a rabbit in his hand") and syllables (repetitive vowel /i/ and continuous vowel /i/). In the scanner, subjects will listen to an auditory example of the task presented in a pseudorandomized order and reproduce it within the 5-s interval of the 'silent' period of scanning, only after which a 2-s image acquisition will follow, while the subjects remain silent and motionless. A resting condition without auditory presentation will serve as a baseline. Four scanning sessions will be acquired with a total of 36 experimental trials and 24 baseline conditions. Structural MRI will be acquired for an anatomical reference.

Data analysis will follow the similar processing pipeline as previously employed by us using AFNI software ([name] et al., 2007; [name] et al., 2009; [name] and Ludlow, 2010). Following initial data processing, the task-related responses will be analyzed using multiple linear regression with a single regressor for each task convolved with a canonical hemodynamic response function. Baseline drifts will be modeled using quadratic polynomials in time for each separate imaging run, and motion parameter estimates will be used as additional regressors of no interest in the multiple regression analysis. To account for disorder-specific vocal motor differences between SD and SD/VT groups, such as adductor and abductor voice breaks and shakiness, respectively, we will include the number of voice breaks and severity of voice tremor as variables in a within-group statistical analysis. Quantitative measures of SD and VT symptoms will be derived from the *Study 1.3.3* within this Aim. The correction of individual statistical parametric maps for multiple comparisons will be performed using Monte-Carlo simulations (Forman et al., 1995), which will identify a minimum cluster size at a voxelwise threshold of 0.005 at overall significance level of a corrected $p \leq 0.025$.

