For group analysis, the 3-D anatomical datasets of each subject will be spatially normalized and converted to the standard anatomical space. The resulting normalization parameters will be applied to the 4-D time series datasets. To estimate the main effect of a task per group, the group analysis will be carried out using a three-way analysis of variance (ANOVA) with subject as a random factor and the task and group as fixed factors ($p \leq 0.025$, voxelwise corrected) to identify (1) shared abnormalities in all patients vs. controls, and (2) distinct abnormalities between SD vs. SD/VT patients. Statistical differences in brain activation extent will be assessed using the subtraction method within the three-way ANOVA design. This univariate data analysis will provide information about the extent and intensity of brain activation in different groups (i.e., SD and SD/VT patients vs. controls and SD patients vs. SD/VT patients).

To further our knowledge of functional brain abnormalities in SD and VT, we will perform multi-stage brain network analysis, which will allow for identification of abnormal brain networks and the relationship between the key network regions, possibly contributing to the pathophysiology of these disorders. For this, we will first perform a correlation analysis between functional and structural datasets in SD and SD/VT patients to determine the brain regions of abnormal function with underlying structural changes. The structural data will be derived from the *Studies 1.3.2 and 1.3.3*.

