Data analysis. Similar to our recent study in SD ([name] and Ludlow, 2011), brain volume in each subject will be segmented into gray matter, white matter, and CSF. VBM analysis will follow the standard procedure using VBM8 toolbox in the SPM8 software. Spatial normalization will be performed using a diffeomorphic nonlinear registration tool (DARTEL) to improve inter-subject registration (Ashburner, 2007). Voxelwise statistical differences in GMV between groups will be examined using independent t -tests with age, gender, total intracranial volume, number of SD-specific voice breaks, severity of tremor and disorder duration as nuisance effects (Ashburner and Friston, 2000). The cluster-level significance will be assessed using a conservative non-stationary cluster extent correction (Hayasaka and Nichols, 2004) at $p \leq 0.025$.

Study population and Sample size. The same 3 groups of SD, SD/VT and healthy control subjects recruited for the fMRI study will participate in this study. To determine the sample size for this study, we reviewed our previous study in 40 SD patients and 40 controls ([name] and Ludlow, 2011). That study found increased GMV in the laryngeal primary sensorimotor cortex (HV vs. SD: 0.22 ± 0.04 vs. 0.26 ± 0.04). Using these values, t -test indicated that a sample size of 17 subjects per group will provide 80% power to detect group differ-

ences at a 0.025 significance level in the present study. To increase statistical power of the proposed studies and account for subjects' dropout possibilities, we will recruit the same 20 subjects per group, who participate in the 1.3.1. *Study #1*.

1.3.3 Study #3: Mapping disorder-specific white matter abnormalities in patients with SD vs. SD/VT using DTI.

In this study, we propose to identify white matter abnormalities contributing to SD and SD/VT using DTI on a 3.0 Tesla Philips scanner. Whole-brain brain images will be acquired using spin-echo EPI sequence with paired gradient pulses for diffusion weighting; diffusion will be measured along at least 33 non-collinear directions. We successfully used a similar scanning protocol in our previous studies ([name] et al., 2008; [name] et al., 2009).

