Data analysis. Diffusion-weighted images will be corrected for eddy current distortions and head motion using affine registration to a reference volume and an individual's T1-weighted image. The diffusion tensor for each voxel will be calculated based on the eigenvectors and eigenvalues using multivariate fitting and diagonalization. Statistical analyses of FA and mean diffusivity (MD) changes between patients and control will be conducted using unbiased whole-brain voxelwise TBSS analysis (Smith et al., 2006) using FSL software as previously described ([name] et al., 2008). Within- and between-group statistical differences in FA and MD for each point of the white matter skeleton will be assessed using univariate GLM design at an adjusted $p \leq 0.025$ to correct for multiple comparisons.

To examine white matter connectivity and its abnormalities in SD and SD/VT patients, we will further use probabilistic tractography (Behrens et al., 2007) in order to identify anatomical connectivity between the regions of the abnormal network as determined in *Study 1.3.1*. To generate a probabilistic streamline and build up the connectivity distribution, the distribution probabilities of each fiber direction will be sampled in each voxel. These calculated local diffusion directions will allow for modeling of multiple fiber orientations in each voxel starting from the seed voxel. To identify the connections between the ROIs, probabilistic tractography will be performed with the following parameters: 5000 streamline samples, 2000 steps with 0.5 mm step length and 0.1-curvature threshold. All resulting probabilistic tractography maps will be averaged to create the group maps normalized to the standard space and thresholded at a corrected $p \leq 0.025$.

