Eligible subjects will be male and female adults of diverse racial and ethnic backgrounds. However, because SD usually occurs between 40 and 55 years of age and predominantly in women and in Caucasians, a higher percentage of Caucasians and women are expected to be recruited. Because the onset of SD is in mid-life, children are not expected to participate. Vulnerable subjects, e.g., cognitively impaired, institutionalized individuals, prisoners, will not be eligible for these studies.

Eligibility for participation will be based on the following criteria.

Inclusion criteria:

1. SD and SD/VT patients will have clinically documented ADSD or ABSD with and without positive effects of alcohol on their symptoms;
2. Healthy controls will be healthy volunteers with a negative history of laryngeal, neurological, or psychiatric problems;
3. Age from 21 to 80 years.
4. Native English speakers.
5. Right-handedness (based on Edinburgh Handedness Inventory).

Exclusion criteria:

1. Subjects who are incapable of giving an informed consent.
2. Pregnant or breastfeeding women until a time when they are no longer pregnant or breastfeeding. All women of childbearing potential will have a pregnancy test performed, which must be negative for participation in the imaging studies.
3. Subjects with past or present medical history of (a) neurological problems, such as stroke, movement disorders (other than SD and VT in the patient groups), brain tumors, traumatic brain injury with loss of consciousness, ataxias, myopathies, myasthenia gravis, demyelinating diseases, alcoholism, drug dependence; (b) psychiatric problems, such as schizophrenia, major and/or bipolar depression, obsessive-compulsive disorder; (c) laryngeal problems, such as vocal fold paralysis, paresis, vocal fold nodules and polyps, carcinoma, chronic laryngitis.
4. Patients who are not symptomatic due to treatment with botulinum toxin injections into the laryngeal muscles. The duration of positive effects of botulinum toxin vary from patient to patient but lasts on average for 3-4 months. All patients will be evaluated to ensure that they are *fully symptomatic* prior to entering the study, except the Study 2.3.2, which will examine the effects of combined botulinum toxin and sodium oxybate treatments on abnormal brain function in SD and SD/VT patients.

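### The fMRI group ANOVA has no age or gender term, and the PPI and TBSS group models list no covariates, although the groups are matched on both and VBM adjusts for both: a possible loss of precision that is cheap to avoid.

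*Combined protocol and SAP*

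**What the plan says.** **Matching (section 1.3).** SD and SD/VT patients are matched "according to their report of alcohol effects, in addition to their age, gender and an SD type match". Controls are matched to the patients on age and gender; the human-subjects section adds ethnicity. The eligibility range is "Age from 21 to 80 years". The same 20 subjects per group serve the fMRI, VBM and DTI studies.

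**VBM (section 1.3.2).** The group t-tests are run "with age, gender, total intracranial volume, number of SD-specific voice breaks, severity of tremor and disorder duration as nuisance effects".

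**fMRI (section 1.3.1).** The group model is a "three-way analysis of variance (ANOVA) with subject as a random factor and the task and group as fixed factors". Two symptom measures are also mentioned: "we will include the number of voice breaks and severity of voice tremor as variables in a within-group statistical analysis". Neither is a matching variable, and they do not enter the between-group contrast.

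**PPI (section 1.3.1).** Subject-level connectivity maps go to within- and between-group analyses at a corrected threshold. No covariates are listed.

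**DTI (section 1.3.3).** FA and MD differences "for each point of the white matter skeleton will be assessed using univariate GLM design". No model terms are listed, and the TBSS method is referred to an earlier publication.

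**The concern.** Matching balances a variable between groups but does not remove its variance within them. If FA or BOLD signal changes with age, that variance stays in the residual unless age is in the model. The usual two-sample standard error then overstates the real uncertainty of a matched difference. So matching makes adjustment more useful; it is not a reason to skip it.

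The plan treats age and gender as worth adjusting for in one modality. It gives no reason for a different treatment of the same subjects in the others. What is at stake is power, mainly for DTI, where 20 per group leaves little margin.

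**Working it through.** **Inputs from the documents.** DTI planning values (1.3.3): FA 0.55 ± 0.05 in patients and 0.61 ± 0.07 in controls, 18 per group for 80% power at 0.025. fMRI planning values (1.3.1): 0.63 ± 0.16 and 0.39 ± 0.23, two-tailed t-test, 15 per group for 80% power at 0.025. Planned recruitment: 20 per group.

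**Standardised effects.**
- DTI: d = 0.06 / √((0.05² + 0.07²)/2) = 0.06 / 0.0608 = 0.986.
- fMRI: d = 0.24 / √((0.16² + 0.23²)/2) = 0.24 / 0.198 = 1.211.

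**The plan's own figures (exact t, unmatched, no covariates).**
- fMRI at two-sided 0.025: 79% power with 14 per group and 82% with 15. The stated 15 is reproduced.
- DTI at two-sided 0.025: the exact t needs 21 per group and the normal approximation 20. The stated 18 is reproduced exactly only at one-sided 0.025. The sidedness is not stated for DTI, and that is a separate matter.
- At 20 per group and two-sided 0.025, power is 78% for DTI and 93% for fMRI.

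Both calculations use unadjusted SDs and take no credit for matching.

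**Effect of the covariates.** Let r be the within-group correlation of the outcome with the matched variables. The documents do not give it, so r = 0.1 to 0.6 is an assumption. The residual SD after adjustment is SD × √(1 − r²), so the unadjusted standard error is too wide by the factor 1/√(1 − r²). Adjusted power uses the noncentral t with d/√(1 − r²) and 40 − 2 − 2 = 36 degrees of freedom. Unadjusted power and actual type I error come from simulating exactly matched pairs, 20 per group, analysed with an ordinary two-sample t-test at two-sided 0.025.

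| r | SE too wide by factor | Actual type I error, unadjusted | DTI power, unadjusted | DTI power, adjusted |
|---|---|---|---|---|
| 0.1 | 1.005 | 2.5% | 78% | 78% |
| 0.2 | 1.021 | 2.2% | 78% | 80% |
| 0.3 | 1.048 | 1.9% | 79% | 82% |
| 0.5 | 1.155 | about 1% | 81% | 89% |
| 0.6 | 1.250 | 0.6% to 0.7% | 83% | 94% |

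Before rounding, the r = 0.2 row is 78.4% against 79.7%, a gain of 1.3 percentage points. If r = 0, the two extra terms lower DTI power from 78.1% to 77.9%.

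**fMRI by the same method.** Unadjusted against adjusted power is 94% against 95% at r = 0.3, and 96% against 99% at r = 0.6.

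**The case against.** **DTI is silent, not explicit.** A reader might infer that the TBSS model leaves age and gender out. The text does not support that: a GLM can carry covariates, and the section points to an earlier description that is not in the documents. This stands. For DTI the terms are unspecified; only the fMRI ANOVA has a stated list of terms without age and gender.

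**The size rests on an assumed correlation.** This also stands. The age limits of 21 and 80 are eligibility bounds, not an expected spread; the plan puts usual onset at 40 to 55 and gives no SD for age. The simulation also assumes exact pair matching, whereas the plan does not say whether matching is by pair or by group. With looser matching the unadjusted test would be less conservative than the table shows.

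**Nothing becomes invalid.** This stands too. The unadjusted test errs on the safe side, and the sample sizes were computed without any gain from matching. fMRI loses little at its planning effect. That effect is SD against controls, however; the plan gives none for SD against SD/VT, so the 93% cannot be carried over to that contrast.

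**Differences between modalities.** It is tempting to say that regional disagreement between VBM and the other maps would only reflect different models. Section 1.3.1 plans a correlation between functional and structural datasets, but it does not say that adjusted group maps are compared. That harm is conjecture.

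What the objections leave untouched is that age and gender are adjusted for in one analysis of these subjects and not named in the others, with no reason given.

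**Conclusion.** The point holds as a free improvement in precision. The fMRI group ANOVA omits age and gender, and the PPI and TBSS group models do not say whether they include them, while VBM in the same matched subjects adjusts for both. For DTI at 20 per group, d = 0.986 and two-sided 0.025, the gain from adjustment runs from nil at r = 0.1, through about 3 percentage points at r = 0.3 and 8 at r = 0.5, to about 11 at r = 0.6. These figures depend on the assumed correlation and on exact matching. For fMRI the case is mainly consistency.

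A reader might conclude that SD type and alcohol response must also be added. The documents do not support that as a matter of consistency: VBM does not adjust for them either, and no figure shows a benefit. With about 20% abductor cases expected, SD type would rest on about 20 × 0.20 = 4 patients per group.

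**What to change.** State the design matrix for the TBSS GLM and for the fMRI and PPI group models, and include age and gender as covariates in each, as VBM already does. The fMRI ANOVA should be written as a model that accepts a continuous between-subject covariate. SD type and alcohol response may be considered for SD against SD/VT, with a reason given, but are not needed to agree with VBM.

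The cost is a change of wording and about 2 degrees of freedom per model, or roughly 0.2 percentage points of DTI power if the covariates turn out to explain nothing. Age and gender must already be recorded for eligibility, matching and VBM, so no new data are needed and the sample size does not change.

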The proposed studies, from univariate analysis to network modeling, are expected to provide full characterization of shared and distinct functional brain abnormalities between SD and SD/VT patients. This approach is feasible in our hand because we have already used similar analysis techniques in our previous studies ([name] et al., 2009; [name] and Ludlow, 2010, 2011).

Study population and Sample size. To estimate the number of subjects to be included in this study, we reviewed our recent fMRI study in SD patients, which used the similar fMRI experimental design ([name] and Ludlow, 2010). Significantly increased activation intensity was found in the primary somatosensory cortex during production of symptomatic syllables in SD patients compared to controls (mean % signal change \pm s.d.: SD vs. controls: 0.63 ± 0.16 vs. 0.39 ± 0.23 ; $p \leq 0.01$). Using these values, results of two-tailed t -test calculations suggest that a sample size of 15 subjects per group would have 80% power to detect group differences at a 0.025 significance level. The power for network analyses is the same. We propose to recruit 20 subjects per group to account for the subjects' dropout possibilities and to increase statistical power for detection of differences between groups.

1.3.2 Study #2: Mapping disorder-specific gray matter abnormalities in patients with SD vs. SD/VT using high-resolution MRI. In this study, we propose to identify GMV abnormalities that are common and distinct between SD and SD/VT patients. VBM is the most commonly used technique to identify changes in both cortical and subcortical gray matter in response to physiological and pathological conditions. To obtain VBM measures, we will acquire whole-brain high-resolution MR images (voxel size ≤ 1 mm isotropic) on a 3.0 Tesla Philips scanner within the same session of fMRI study described above.

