Study population and Sample size. To estimate the number of subjects in this study, we reviewed our recent DTI studies, which used a similar experimental design to examine white matter abnormalities in SD patients and controls ([name] et al., 2008; [name] et al., 2009). Significantly decreased FA was found in the right genu of the internal capsule in SD (patients vs. controls: 0.55 ± 0.05 vs. 0.61 ± 0.07). Using these values, a power of 80% at a 0.025 significance level will be obtained with 18 subjects per group for the proposed study based. Again, to increase the statistical significance and allow for between-study comparisons, we propose to recruit the same 20 subjects per SD, SD/VT and control group for the DTI study. The statistical power for tractography is the same.

1.3.4 Study #4: Relationship between brain abnormalities and clinico-behavioral characteristics in SD and SD/VT.

The role of neuroimaging studies in elucidation of pathophysiological mechanisms of SD would be considerably enhanced if coupled with strategies that yield information about their relevance to symptom elicitation. Additionally, identification of disorder-specific brain abnormalities that are correlated with disorder symptoms can prove useful for assessment of efficacy of existing and newly developed therapeutic interventions. Our approach here will be to examine the relationships of functional brain activity and structural brain organization with clinico-behavioral correlates (i.e., disorder severity scores). For all 20 subjects per group (both patients and controls), the behavioral measures will be obtained during initial intake screening, history and physical examination, and three-tiered diagnostic questionnaire (see *Appendices 1 and 2*). Patients' voice and speech will be digitally recorded during scanning for offline acoustic analysis to assess the SD and VT severity.

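### Tractography in Study 1.3.3 has no named group test and no between-group contrast, so as written it cannot show abnormal or disorder-specific connectivity, and its power claim is unsupported

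*Combined protocol and SAP*

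**What the plan says.** Section 1.3.3 (Study #3), Data analysis, has two parts.

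- **Skeleton analysis (TBSS).** "Within- and between-group statistical differences in FA and MD for each point of the white matter skeleton will be assessed using univariate GLM design"; the significance level is 0.025 after adjustment.
- **Tractography.** The purpose opens: "To examine white matter connectivity and its abnormalities in SD and SD/VT patients, we will further use probabilistic tractography". The same sentence goes on to the operational task, which is to identify anatomical connections between regions of the abnormal network found in Study 1.3.1. After the tracking settings (5000 samples, 2000 steps, 0.5 mm step length), the one group-level instruction is: "All resulting probabilistic tractography maps will be averaged to create the group maps normalized to the standard space and thresholded at a corrected" level of 0.025.

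The sample-size paragraph of 1.3.3 bases its number on FA in the right genu of the internal capsule ("patients vs. controls: 0.55 ± 0.05 vs. 0.61 ± 0.07"). It states that "a power of 80% at a 0.025 significance level will be obtained with 18 subjects per group", plans 20 per group, and closes: "The statistical power for tractography is the same".

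**The concern.** Calling a connection abnormal requires a comparison with controls. Calling it disorder-specific requires a comparison of SD with SD/VT. The tractography text supplies neither, and it does not say which statistic the corrected p-value belongs to. What comes out is a thresholded map per group.

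If no contrast is added, the only way to use these maps for the abnormality question is to note that a connection passes the threshold in one group and not in another. That is not a test of a difference between groups. The stake is interpretive: section 1.4 expects each disorder to show its own pattern of functional and structural alteration, and expects the findings to serve as imaging markers for differential diagnosis. A tractography result without an error rate for group differences should not feed into that.

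The power sentence adds to the problem, because it tells the reader that a tractography comparison with 80% power exists.

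**Working it through.** **1. Is a group comparison of tractography written anywhere?** The analyses of Specific Aim #1, side by side:

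| Analysis | Section | Between-group test stated? |
|---|---|---|
| fMRI activation | 1.3.1 | Yes: ANOVA; patients vs controls, SD vs SD/VT |
| PPI connectivity | 1.3.1 | Yes: group analyses within and between groups |
| DCM connectivity | 1.3.1 | Yes: SD and SD/VT vs controls; SD vs SD/VT |
| VBM gray matter | 1.3.2 | Yes: independent t-tests between groups |
| FA and MD on the skeleton | 1.3.3 | Yes: univariate GLM |
| Tractography | 1.3.3 | No: average, then threshold |
| Symptom correlations | 1.3.4 | Not a group comparison; correlations within each patient group |

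Section 1.1 states a general intention to study structural networks in SD vs SD/VT vs controls, but gives no tractography method. The gap is specific to tractography.

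**2. What could the corrected p-value refer to?** The likeliest candidate is a one-sample test across the 20 subjects of a group. It is feasible, since between-subject variance exists at each voxel. Streamline counts cannot be negative, however, so a test that their mean exceeds zero says little. At best it shows where a group has a connection. It does not compare groups.

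**3. The plan's own sample size (FA).** Inputs from the sample-size paragraph of 1.3.3:

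- difference = 0.61 − 0.55 = 0.06
- pooled standard deviation = √[(0.05² + 0.07²)/2] = √0.0037 = 0.0608
- standardised difference = 0.06 / 0.0608 = 0.986

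Two-sample t-test results:

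| Level | n per group for 80% | Power at 18 | Power at 20 |
|---|---|---|---|
| one-sided 0.025 (equivalent to two-sided 0.05) | 18 | 82.0% | 86.0% |
| two-sided 0.025 | 21 | 72.8% | 78.1% |

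The stated 18 reproduces at one-sided 0.025. Section 1.3.1 uses two-tailed tests at 0.025 for its 15 per group, and on that convention 18 would fall short. This is a side observation on FA; the present point does not rest on it.

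**4. Can this power be carried over to tractography?** Power needs an outcome, an effect size, a contrast and a significance level. For tractography:

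- outcome: none defined
- mean and standard deviation: none given
- contrast: none given, and the FA figures are patients vs controls only, so they say nothing about SD vs SD/VT
- level: the FA calculation is one comparison at 0.025; with a family-wise correction over more than one region pair, a single pair would face a stricter level

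Tractography power is therefore not computable from the documents, in either direction.

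**5. Illustration of what comparing thresholded maps would do (assumed values).** Suppose two independent groups have identical true connectivity, and each passes the threshold with probability q. The chance that exactly one passes is 2q(1 − q). For q = 0.8 this is 2 × 0.8 × 0.2 = 32%; for q = 0.5 it is 2 × 0.5 × 0.5 = 50%. Neither is close to 0.025. The plan does not say that maps will be compared this way; the figures only show why a contrast is needed.

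**The case against.** Four points can be made on the other side.

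- **A p-value is possible.** A reader might infer that an averaged map has no test behind it and that the threshold is meaningless. That goes too far. With about 20 subjects per group, a corrected one-sample or permutation test of the mean map could be run. The test is unnamed, not impossible.
- **Part of the purpose is met.** A reader might infer that the tractography goal fails outright. The purpose sentence also asks which regions of the network are anatomically connected, and within-group maps can answer that.
- **White matter abnormality is tested elsewhere.** A reader might infer that the DTI study has no group comparison. It does, for FA and MD, and PPI and DCM have their own. Tractography is an addition within one of four Aim #1 studies, and Specific Aim #2 does not use it.
- **Harm is not stated.** No section says that maps will be compared by eye. Section 1.1 and the power sentence suggest that a comparison was intended and its method left out.

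All four stand as limits on the point. None supplies the missing contrast. The FA and MD tests do not measure connectivity between region pairs, and an intention to compare does not tell the analyst what to compare or how to control error.

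**Conclusion.** The point holds in this form. For tractography the plan names no test statistic and no patient-versus-control or SD-versus-SD/VT contrast. Followed as written, the step can map connections within a group but cannot show that connectivity is abnormal or differs between the disorders, which is part of its stated purpose. The claim of equal power is unsupported, because it borrows an FA difference of 0.06 (standardised 0.986) for a test that is not defined.

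The size cannot be put as a number: the group-difference error rate and the power of the tractography step are both unspecified, against a stated 0.025 and 80%. The documents do not support saying that the threshold is impossible, that the whole goal is out of reach, or that the DTI study lacks group tests. The conclusion assumes that no tractography contrast is written outside the sections compared above; none was found. The change is worth making but concerns a supporting analysis, and it affects neither recruitment nor the sodium oxybate results.

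**What to change.** In 1.3.3, Data analysis, replace the group-level tractography sentence with a specified comparison:

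1. **Outcome.** For each subject and each pair of network regions, derive one connection measure from the planned 5000-sample run, for example the proportion of streamlines sent from the seed that reach the target. Other subject-level measures would also serve; what matters is that one is named in advance.
2. **Contrasts.** Use those already stated for DCM: SD and SD/VT vs controls, and SD vs SD/VT.
3. **Model.** Use a GLM on the subject-level measure. Age and gender may be added as covariates; the DTI section does not now include them, so this would be a new choice to state.
4. **Multiplicity.** Name the correction across region pairs at 0.025, for example permutation-based. The DTI section says only that p is adjusted, so the method cannot be taken over by reference.
5. **Maps.** Keep the averaged maps for display only.
6. **Power.** In the sample-size paragraph, delete the tractography power sentence or state that this analysis is not separately powered.

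The cost is a little more analysis of data already to be collected, a few sentences of plan text, and the loss of a stated power figure. No extra subjects or scans are needed.
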